14.4 Electrocardiogram (ECG)

The summary of ECG will only include on treatment data, which are defined as those ECG measurements after the first dose of study treatment and on or before last dose + 84 days.

The following quantitative variables will be summarized: ventricular rate, RR interval, PR interval, QRS duration, QT interval, and corrected QT interval (QTc). Both Bazett (QTcB) and Fridericia (QTcF) corrections will be presented for QTc.

QTc will only be summarized by computing the number and percentage of subjects (including 95% confidence intervals for pooled analyses, e.g. DMC or SCS) with:

- QTc > 500 msec
- QTc > 480 msec
- QTc > 450 msec
- QTc changes from baseline > 30 msec
- QTc changes from baseline > 60 msec
- PR > 250 msec

Subjects with notable abnormal ECG parameters as described above, after baseline will be summarized.

Summary statistics will be presented for ECG variables by visit and treatment dose in safety population.

Shift tables comparing baseline ECG interpretation (normal, abnormal, not available, total) with the worst on-study interpretation (normal, abnormal, not available, total) will be provided.

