In addition, shift tables will be provided for all parameters to compare a subject's baseline laboratory evaluation relative to the visit's observed value. For the shift tables, the normal laboratory ranges will be used to evaluate whether a particular laboratory test value was normal, low, or high for each visit value relative to whether or not the baseline value was normal, low, or high. These summaries will be presented by laboratory test and treatment group. Shifts will be presented by visit as well as for most extreme values post-baseline.

[figure not shown]
Vital signs

Analysis of the vital sign measurements using summary statistics for the change from baseline for each post-baseline visit will be performed. These descriptive summaries will be presented by vital sign and treatment group. Change from baseline will only be summarized for subjects with both baseline and post-baseline values.

ECG

Summary statistics will be presented for ECG variables by visit and treatment group. Qualitative changes will be summarized.

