3.2 Secondary objectives

1. To evaluate the long-term efficacy of secukinumab with respect to:
 - a. Changes in HAQ-DI relative to baseline over time up to Week 260
 - b. The proportion of subjects with improvements from baseline in HAQ-DI meeting or exceeding minimal clinically important difference (MCID) over time up to Week 260
 - c. The changes in DAS28 (utilizing hsCRP) relative to baseline over time up to Week 260
 - d. The proportion of subjects achieving low disease activity ($\text{DAS28} \leq 3.2$) and disease remission as defined by DAS28 ($\text{DAS28} < 2.6$) over time up to Week 260
2. To evaluate the long term safety and tolerability of secukinumab 75 mg and 150 mg as assessed by vital signs, clinical laboratory variables, and adverse events monitoring over time up to Week 260.

4 Data presentation

Data analyses will be presented by treatment groups or treatment sequence as appropriate

Unless otherwise stated, summary tables/figures/listings will be on all subjects included in the population under consideration.

Summary statistics for continuous variables will include N, mean, standard deviation, minimum, lower quartile, median, upper quartile, maximum. Summary statistics for discrete variables will be presented in contingency tables and will include absolute and relative frequencies.

For categorical or binary variables, the number and percent of subject in each category will be presented. The p-values if presented will be two-sided unless otherwise specified, and 95% confidence intervals will be provided as appropriate.

In general, efficacy data from the extension study period will be reported for clinical study report (CSR) and publication(s). Baseline from core and Week 104 visit data will be presented appropriately. No formal hypotheses testing will be done. Hence, the p-values and confidence intervals provided should be considered as exploratory only.

Safety data from core and extension studies will be reported cumulatively for CSR and publication(s). Placebo safety data from core will not be reported in post text tables.

All listings will be presented by treatment groups. Safety listings will also include the placebo data.

5 Subjects and treatments

The following analysis sets will be used for the data analysis:

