Summaries for newly occurring or worsening clinically notable lipid abnormalities will also be provided cumulatively for each of the following parameters and categories:

- HDL:
 - ≤LLN
 - <0.8 x LLN
- LDL, cholesterol, triglycerides:
 - ≥ULN
 - >1.5 x ULN
 - >2.5 x ULN

Newly occurring or worsening liver enzyme abnormalities will also be summarized based on the event criteria given in [Table 14-3](#):

Table 14-3 Liver-related events

Parameter	Criterion
ALT	>3xULN; >5xULN; >8xULN; >10xULN, >20xULN
AST	>3xULN; >5xULN; >8xULN >10xULN; >20xULN
ALT or AST	>3xULN; >5xULN; >8xULN >10xULN; >20xULN
TBL	>1.5xULN, >2xULN, >3xULN,
ALP	>2xULN, >3xULN. >5xULN
ALT or AST & TBL	ALT or AST >3xULN & TBL >2xULN; ALT or AST >5xULN & TBL >2xULN; ALT or AST >8xULN & TBL >2xULN; ALT or AST >10xULN & TBL >2xULN
ALP & TBL	ALP >3xULN & TBL >2xULN ALP >5xULN & TBL >2xULN
ALT or AST & TBL & ALP	ALT or AST >3xULN & TBL >2xULN & ALP <2xULN (Hy's Law) Note: elevated ALP may suggest obstruction as a consequence of gall bladder or bile duct disease; ALP may also be increased in malignancy. FDA therefore terms Hy's Law cases as indicators of pure hepatocellular injury . This does not mean that cases of ALT or AST >3xULN & TBL >2xULN & ALP ≥2xULN may not result in severe DILI.

Notes: 1) In studies which enroll subjects with pre-existing liver disease, baseline LFT may be increased above ULN; in such a case it is meaningful to add the condition “and worse than baseline” to the abnormality criteria

For a combined criterion to be fulfilled, all conditions have to be fulfilled on the same visit. The criteria are not mutually exclusive, e.g. a subject with ALT = 6.42xULN is counted for ALT >3xULN and ALT >5x ULN.

Individual subject laboratory data listings will be provided for all subjects as well as for subjects with newly occurring or worsening CTCAE grades, or with newly occurring or worsening after baseline abnormalities in lipid parameters, or with newly occurring or worsening after baseline abnormalities in liver enzymes.

No box plots over time or other graphs will be presented for any of the laboratory parameters.

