14.3 Vital signs

The summary of vital signs will only include on treatment data, which are defined as those vital sign measurements after the first dose of study treatment and on or before last dose + 84 days.

Analysis in vital sign measurement using descriptive summary statistics for the change from baseline for each post-baseline visit in extension only be presented for subjects with both a baseline (of core study) and post baseline values. These descriptive summaries will be presented by vital sign and treatment dose. Change from baseline will only be summarized for subjects with both baseline and post-baseline values and will be calculated as:

$$\text{change from baseline} = \text{post-baseline value} - \text{baseline value}$$

Analysis in vital sign measurements using descriptive summary statistics for the change from baseline until each post-baseline visit will be performed.

The number and percentage of subjects with newly occurring notable vital signs will be presented. Criteria for notable vital sign abnormalities are provided in [Table 13-4](#) below.

Table 14-4 Criteria for notable vital sign abnormalities

Vital sign (unit)	Notable abnormalities
Systolic blood pressure (mmHg)	>= 140 mmHg or < 90 mmHg
Diastolic blood pressure (mmHg)	>=90 mmHg or <60 mmHg
Pulse (bpm)	> 100 bpm or <60 bpm

Individual subject listing of vital signs and a listing for the newly occurring notably abnormalities will be provided.

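### SAP 14.4 counts absolute QTc and PR limits met after baseline without excluding, or showing separately, subjects who already met them at core baseline

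*SAP*

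**What the plan says.** SAP 14.4 lists six ECG criteria. Four are absolute (QTc above 450, 480 and 500 msec; PR above 250 msec). Two are relative to baseline: "QTc changes from baseline > 30 msec" and the same at 60 msec. It then states: "Subjects with notable abnormal ECG parameters as described above, after baseline will be summarized". It also plans "Shift tables comparing baseline ECG interpretation (normal, abnormal, not available, total) with the worst on-study interpretation".

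The neighbouring sections are worded differently. For vital signs, SAP 14.3 says "The number and percentage of subjects with newly occurring notable vital signs will be presented". For liver tests, SAP 14.2 says "Newly occurring or worsening liver enzyme abnormalities will also be summarized", and its lipid table follows the same rule.

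Three general rules bear on how the ECG counts are read:

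- SAP Table 14-1 labels the vital-sign and ECG notables as crude incidence, which SAP 17.3.3.1 defines for subjects at risk of the event.
- SAP section 7 fixes baseline at the last value before the first dose in the core study.
- The opening of SAP section 14 counts a subject who switches or escalates in both groups, using the exposure dates for each.

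**The concern.** An incidence table should show what arose on treatment. For the four absolute limits, the ECG table mixes new crossings with abnormalities present before the first dose. A subject with PR 260 msec before any drug who still has PR 260 msec on treatment is a notable finding under this wording.

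The dose columns can repeat the same abnormality. Baseline is always core baseline, and escalation from 75 to 150 to 300 mg is allowed (Protocol 3.1). A subject over the limit before treatment can therefore appear under each dose at which a further ECG exceeds it. Escalation is at the investigator's judgement, so the share of such subjects may differ between columns for reasons unrelated to the drug. A reader comparing doses could take a difference in baseline mix for a difference in ECG effect.

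**Working it through.** **No figure to reproduce.** The documents give no ECG rate, QTc mean or SD, or baseline prevalence. Everything below is illustrative.

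**Identity.** Let b be the share over the limit at baseline, r the probability that such a subject is over it again on treatment, and i the new-onset risk in the rest.

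- Reported under SAP 14.4: R = b·r + (1−b)·i
- Newly occurring among those at risk: i
- Pre-existing share of those counted: b·r / R

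**Assumed inputs.** Normal QTc with no drug effect; mean 410 or 420 msec; between-subject SD 18 or 20; within-subject SD 10 or 12; 4 or 8 post-baseline ECGs. All 16 combinations were simulated.

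**Baseline share above 450.** b = 1 − Φ[(450 − mean)/√(SD_between² + SD_within²)].

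- Lowest: (450−410)/√(18²+10²) = 40/20.59 = 1.94, so b = 2.6%.
- Highest: (450−420)/√(20²+12²) = 30/23.32 = 1.29, so b = 9.9%.

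**Effect on the >450 row at the two extremes of the grid**

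| Mean, SDs, ECGs | b | r | i | R | Pre-existing share | R/i |
|---|---|---|---|---|---|---|
| 410, 18/12, 8 | 3.2% | 0.78 | 9.8% | 12.0% | 21% | 1.23 |
| 420, 20/10, 4 | 9.0% | 0.83 | 11.2% | 17.6% | 42% | 1.57 |

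Second row by hand: b·r = 0.090 × 0.826 = 0.074; (1−b)·i = 0.910 × 0.112 = 0.102; R = 0.176; share = 0.074/0.176 = 0.42; R/i = 0.176/0.112 = 1.57.

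Across the grid, r runs from 0.66 to 0.91. More readings lower the share: in the second row it falls from 42% with 4 ECGs to 36% with 8. The extension schedules six (Weeks 128, 156, 180, 208, 232 and 260) and core ECGs add to these, so a completer's share could lie towards or below the lower end.

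**Higher limits.** For 480 msec the same formula gives b from 0.03% (70/20.59 = 3.40) to 0.5% (60/23.32 = 2.57). Even in all 606 core subjects that is about 0.2 to 3 people. For 500 msec, b is at most 0.03% (80/23.32 = 3.43), which is fewer than one. PR was not modelled.

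**Sensitivity without a distribution.** Fix i = 3%.

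- b = 1%, r = 0.5: R = 0.005 + 0.99 × 0.03 = 3.5%, pre-existing share 14%.
- b = 10%, r = 0.9: R = 0.09 + 0.90 × 0.03 = 11.7%, pre-existing share 77%.

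The direction is fixed whenever r exceeds i. The size depends on b, r and i.

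**The case against.** The best case for leaving the ECG table alone has three parts. First, it is described as findings after baseline, not as new onset, and an inclusive count is a legitimate safety display. Second, two of the six rows are already changes from baseline, and a baseline-to-worst shift table is planned. Third, these are descriptive tables with no hypothesis test; baseline values are to appear in by-visit summaries, and placebo data in in-text tables and listings.

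Much of this is fair and limits the consequence, but it does not remove the point. The label in Table 14-1 is crude incidence. The shift table uses overall normal or abnormal interpretation, not these limits. The >30 and >60 msec rows do not show who crossed 450, 480 or 500, and PR has no change row.

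The objection is also right that a bare new-onset rule loses information. A subject moving from 455 to 478 msec would be excluded from the >450 row, would not reach 480, and would have changed by only 23 msec. Any fix has to keep such subjects visible.

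Three stronger readings are tempting, and the documents do not support them:

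- **That the vital-sign percentages are diluted by subjects already abnormal at baseline.** SAP 14.3 states no denominator. SAP section 4 says "Unless otherwise stated, summary tables/figures/listings will be on all subjects included in the population under consideration", which points to everyone in the safety set. SAP 17.3.3.1 defines crude incidence for subjects at risk, yet also calls n the total number of subjects. On the all-subjects reading, the percentage is (1−b) times the at-risk incidence (0.9 times at b = 10%, 0.6 times at b = 40%). On the at-risk reading there is no bias. This is missing detail, not a stated error.
- **That a subject high at baseline cannot later be a new low case.** The systolic criterion reads ">= 140 mmHg or < 90 mmHg". Nothing says that meeting one side blocks the other, and newly occurring is not defined.
- **That the SAP departs from the protocol.** Protocol 9.5.2 says of ECG "Qualitative changes will be summarized". The planned shift tables meet that.

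**Conclusion.** The point holds for the four absolute ECG limits and no further. As written, SAP 14.4 lets pre-treatment QTc and PR abnormalities count as on-treatment findings, possibly in more than one dose column, while the vital-sign, lipid and liver tables are worded to avoid this.

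Under the assumed QTc model, about a fifth to two fifths of subjects in the >450 row would be pre-existing, and the reported rate would be 1.2-1.6 times the new-onset rate. The effect on the >480 and >500 rows would be at most a few subjects. These sizes rest wholly on assumed inputs; the trial's own baseline ECGs would settle them. With no formal testing at stake, this is a cheap improvement to the safety tables and not a threat to the trial's conclusions. On vital signs, the most that can be asked is a clarification.

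**What to change.** In SAP 14.4:

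- Report each absolute QTc and PR limit as newly occurring, meaning not met at core baseline. Show n/m, with m the subjects who have a baseline and a post-baseline ECG and did not meet that limit at baseline.
- Show subjects already over the limit at baseline in a separate row, or in a shift table of baseline category against worst post-baseline category using the same cut-offs, so that worsening is not lost.
- Keep the >30 and >60 msec change rows as they are.

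In SAP 14.3, as a clarification only, define newly occurring separately for the high and low limit of each vital sign and state the denominator.

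The cost is SAP wording and minor programming on data already collected. The downside is that denominators differ by row and there is one extra row or table. The change does not settle which dose is credited when a subject first crosses a limit before escalation and stays over it afterwards; the general rule at the start of SAP section 14 still governs that.

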14.5 Immunogenicity

A listing of immunogenicity (anti-AIN457 antibodies) and a table with an overview of patients with anti-drug antibodies for patients with baseline or treatment emergent ADA will be provided.

14.6 Compound specific safety evaluation

Safety topics of interest, such as risks defined in the Safety Profiling Plan, Risk Management Plan or topics of interest regarding signal detection or routine analysis are defined in the Program Case Retrieval Sheet that is stored in CREDI at the path Cabinets/CREDI Projects/A/AIN457A/Integrated Medical Safety.

The crude incidence and exposure-adjusted incidence rates for potential compound and class-related risks and routine risks will be summarized. In addition, listings will be provided presenting which subjects experienced which risk.

Important note: For the evaluation of SPP risks primary and secondary system organ classes of the MedDRA dictionary will be considered.

15 Interim analyses

Interim analyses are planned in order to support regulatory filing and for purposes of publication after subjects complete year 1 (Treatment period 3), and year 2 (Treatment period 4) of treatment in this extension study. Additional analyses may be performed to support health authority interactions, as necessary.

16 Sample size calculation

It is estimated that 80~90% of subjects originally randomized to secukinumab will complete the entire treatment period and be eligible for entry into the extension (320~360 subjects). Likewise, 70~80% of the subjects originally randomized to placebo (140~160 subjects) will be eligible. In total, it is estimated that 460~520 subjects will be eligible for enrollment in this extension study.

17 Appendix

17.1 Visit Windows

When visit windows are used, all visits will be re-aligned, i.e., they will be mapped into one of the visit windows. E.g., if the *Week 112* visit of a subject is delayed and occurs on Day 810 instead of on Day 785, say, it will be re-aligned to visit window *Week 116*. In the case of major deviations from the visit schedule, or due to unscheduled visits, several assessments of a subject may fall in a particular visit window (either scheduled or unscheduled or optional site visits). Statistical approaches to handle multiple assessments in a given visit window are specified below.

For lab/ECG/vital signs, follow-up (F/U) visit is excluded from analysis visit mapping window. Only assessments that come as F/U nominal visit will be directly assigned as analysis F/U visit. Other assessments that are beyond the last on-treatment visit window (W264) or after nominal F/U visit date won't be mapped to any analysis visit. F/U visit will not be included in the summary tables by visit.

For visits that occur after week 104 only the recorded nominal visit should be used.

Of note, subjects are allowed to have gaps in visits. Optional site visits will not be presented in summaries but will be used for mapping to planned visits. All data collected will be displayed in listings.

Analysis Visit	Target Day	Analysis Visit Window	Group 1	Group 2	Group 3	Group 4	Group5	Group6	Group7	Group8	Group9	Group1 0	Group1 1	Group1 2	Group1 3	Group1 4	Group1 5
Week 60	421	408-435	394-449	394-449				394-449	394-449							394-449	394-449
Week 64	449	436-463															
Week 68	477	464-491	450-505	450-505				450-505	450-505							450-505	450-505
Week 72	505	492-519															
Week 76	533	520-547	506-561	506-561				506-561	506-561		450-631					506-561	506-561
Week 80	561	548-575															
Week 84	589	576-603	562-617	562-617				562-617	562-617						478-659	562-617	562-617
Week 88	617	604-631															
Week 92	645	632-659	618-687	618-687				618-687	618-687							618-687	618-687
Week 96	673	660-687															
Week 100	701	688-715															674-715
Week 104	729	716-743	688-743	688-743	450-743	548-743	548-743	688-743	688-743	548-743	632-743	548-743	548-743	548-743	660-743	688-743	716-743

Group1: ACR components, HAQ-DI, Tender and Swollen Joints
 Group2: Hematology, blood chemistry, urinalysis, skin test
 Group4: WPAI-GH, cardiovascular panel
 Group5: PK
 Group6: [REDACTED]
 Group7: [REDACTED]
 Group8: [REDACTED]
 Group9: Lipids
 Group10: ECG
 Group11: X-ray

Analysis Visit	Target Day	Analysis Visit Window	Group 1	Group 2	Group 3	Group 4	Group5	Group6	Group7	Group8	Group9	Group1 0	Group1 1	Group1 2	Group1 3	Group1 4	Group1 5
Group12: Immunology, [REDACTED] Group13: Weight Group14: Pregnancy test, hormones Group15: Vital signs																	
* The first administration of randomized study treatment (first dose) is defined as 1.																	

The following rules are used to determine the window for an applicable visit post baseline: “Lower limit” = “upper limit of prior applicable visit” + 1. “Upper limit” = “target day of current visit” + integer part of (“target day of next applicable visit” – “target day of current visit”)/2. Lower limit of the first applicable visit is always Day 2.

The mapping described above applies to all visits including optional site visits (not just scheduled visits). Optional site visits, repeat and/or unscheduled visits (which will be numbered in the database according to new NCDS standards) will be mapped for analysis purposes in the same way as scheduled visits. This leaves the possibility, then, for multiple measurements within an analysis window. The following conventions will be used to determine the appropriate measurement to be summarized in the event of multiple measurements within a visit window.

Table 17-2 Rules for flagging variables

Timing of measurement	Type of data	Rule
Baseline of core	All data	The last measurement made prior to administration of the first dose of study treatment in core– note this may include measurements taken on the day of randomization (e.g. lab). If a patient did not receive any dose of study treatment then the randomization date will be used.
Post-baseline efficacy	All data	The measurement closest to the target will be used. In the event two measurements are taken equally apart (e.g. 1 before target date and 1 after) the first one will be used.
Post-baseline safety	Summary visit information (e.g. lab, ECG, etc.)	The measurement closest to the target will be used. In the event two measurements are taken equally apart (e.g. 1 before target date and 1 after) the first one will be used.
Post-baseline safety	Notable abnormalities (e.g. lab)	The most extreme measurement in the window will be used. Note this means a patient can have a notably high and notably low measurement within a window.

No visit windows were used in case of up-titrations. The before up-titration measurement is considered as the last visit measurement, performed on or before the date that patient took the up-titration dose. The up-titration data analysis will be based on week intervals; it is accounting for the time period between the actual date of exposure to the up-titrated dose and the last visit date of the subject:

- 4 – 8 weeks after up-titration
- 12 – 32 weeks after up-titration
- 36 – 56 weeks after up-titration
- 60 – 80 weeks after up-titration
- 84 – 104 weeks after up-titration

